Cover page

Official Title: An interactive advance care planning intervention to facilitate a good death for
cancer patients

NCT number: NCT01912846

Date of the Document: 2018/1/24

Specific Aims: The primary objectives of this 5-year randomized controlled trial (RCT) of a theory-based, tailored, multifaceted, interactive advance care planning (ACP) intervention are to examine the extent to which the proposed ACP intervention will (1) increase the congruence between terminally ill cancer patients' preferred and actual end-of-life (EOL) care, (2) improve quality of life (QOL), depressive and anxiety symptoms of patients and caregivers during the patient's dying process, and (3) enhance family caregivers' bereavement adjustment. The secondary objectives are to determine the effectiveness of the proposed ACP intervention in facilitating patients' prognostic awareness and EOL care discussions among patients, families, and physicians; in increasing patient-caregiver agreement on preferences for EOL care; and in reducing aggressive EOL care treatments for terminally ill cancer patients.

A randomized controlled trial with a tailored, multifaceted ACP intervention will be conducted on a convenience sample of 231 dyads of terminally ill cancer patients and caregivers with the same number of attention controlled group to evaluate the intervention's effectiveness.

We hypothesize that the proposed intervention will (1) facilitate terminally ill cancer patients' prognostic awareness; EOL care discussions among patients, family caregivers, and physicians; and patient-caregiver agreement on preferences for EOL care as death approaches; (2) reduce aggressive healthcare resource utilization at EOL; (3) increase congruence between the patient's preferred and actual EOL care; (4) improve QOL, depressive and anxiety symptoms of patients and family caregivers during the patient's dying process; and (5) enhance family caregivers' bereavement adjustment. We also hypothesize that the proposed intervention will facilitate patients' prognostic awareness and EOL care discussions among patients, families, and physicians; increase patient-caregiver agreement on preferences for EOL care; and reduce aggressive EOL care treatments for terminally ill cancer patients.

Eligibility criteria for terminally ill cancer patients: (1) diagnosed with a terminal stage disease that continues to progress with distant metastases and judged by their oncologists as

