unresponsive to current curative cancer treatment, (2) cognitively competent, (3) able to communicate with data collectors, (4) age>20 years, and (5) having a designated family caregiver who agrees to participate in the survey. Family caregivers will be recruited if they are: (1) family members of cancer patients with a terminally ill disease as defined by this proposed study, (2) identified by patients as the primary person caring for the patient without financial reimbursement for that care, (3) age>20 years, and (4) agree to participate and can communicate with data collectors. Patients and family caregivers will be excluded if they participate in other research to facilitate prognostic awareness, ACP, QOL, or psychological well-being.

Sample size calculation: There was no interventional study directly investigating the effectiveness in increasing the extent of congruence between patient preferred and actual end-of-life (EOL) care received by terminally ill cancer patients; therefore sample size estimation will be based on the effectiveness of holding EOL care discussions between patients and physicians on the extent to increase congruence between the patient's preferred and actual EOL care received. Patients who reported having EOL care discussions with their physicians significantly more likely to receive EOL care consistent to their preferences (OR=2.26; $p<.0001$) and received significantly fewer aggressive medical interventions near death, with lower rates of CPR (0.8% vs 6.7%; AOR, 0.16; 95% CI, 0.03-0.80), mechanical ventilation support (1.6% vs 11.0%; AOR, 0.26; 95% CI, 0.08-0.83), and ICU care (4.1% vs 12.4%; AOR, 0.35; 95% CI, 0.14-0.90), respectively. A sample size of 124-195 dyads per group achieves 80% power to detect a difference between the interventional and control group by a two-sided hypothesis test with a significance level of 0.05. In compensating the 18.5% of attrition rate found in our previous longitudinal study, 147-231 dyads per group are needed. The proposed sample size will be targeted on 231 dyads per group to ensure adequate power to detect the hypothesized effects of the proposed intervention. Approximately 8-10 new dyads of terminally ill cancer patients and their family caregivers were recruited in each month. In order

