Physicians caring for participants in the intervention group will receive individualized 1-page patient- and family caregiver-specific feedback forms, based on interview responses, to facilitate EOL care discussions with terminally ill cancer patients and their family caregivers. The patient- and family caregiver-specific feedback forms will be generated using an automated, computerized process that reflects the patient's or family caregiver's reported responses, including whether he/she knows the patient's prognosis, her/his desire/readiness to engage in ACP, and preferences for specific EOL care treatments,¹²² including goals of EOL care (comfort-oriented or life-prolonging) and when or if the patient/family caregiver prefers to receive ICU care, CPR, intubation with mechanical ventilation support, intravenous nutrition or hydration, hemodialysis, and hospice care. The trained ACP interventionist will build rapport with physicians caring for participants in the intervention group to provide feedback and to reinforce physicians' communication with participants, help them manage patients' and family caregivers' negative emotional reactions, and minimize their time constraints in delivering sensitive information by facilitating and coordinating EOL care discussions.

Terminally ill cancer patients often poorly understand EOL treatments, including ICU care, CPR, and intubation with mechanical ventilation support, and may overestimate their probability of survival.^{7,110,115} One focus of this proposed ACP intervention is to promote realistic and achievable goals for EOL care and to improve patients' and family caregivers' understanding of the patient's medical situation and the efficacy of life-sustaining treatments proposed at EOL. The ACP intervention will therefore include a workbook and a video to enhance participants' understanding of the essential elements in ACP. The two-part workbook is derived from Pearlman and colleagues'¹²⁰ work. The first part contains basic information on ACP, including life-prolonging and comfort-oriented care, and facts about the probability of survival after and consequences of ICU care, CPR, and intubation with mechanical ventilation support. This information is designed to motivate participants in the precontemplation and contemplation stages of readiness to engage in ACP. The second part contains four subsections:

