procedures provided to subjects in the ACP intervention and attention-control groups will be reviewed by an independent research staff every 3 months to check the extent to which they are consistent with the group protocol. To this end, the research staff will interview randomly selected patient-caregiver dyads in each study group. Third, the workbook and video will be created systematically, starting with a review of the ACP literature in advanced cancer. The workbook content and overall video design will be reviewed for appropriateness and accuracy by 2 physicians specializing in cancer care, 1 ICU physician, 1 expert in palliative medicine, and 1 nurse with expertise in clinical decision-making.

Data collection procedures: Assessments will be performed prospectively and continue until patient death, loss to follow-up, study withdrawal, or when the patient can no longer be interviewed. An every-3-week time frame will be used in this study for repeated QOL and other outcomes assessments for both patients and their family caregivers bases on the review of literature to cover the most rapid change of patient physical conditions and demanding period of caregiving until the death of the patient. After each patient's death, a chart review and postmortem interview with patients' caregivers will be performed to confirm the type of medical care received at the EOL. Bereavement interviews will be conducted 1, 3, 6 and 13 months after the time of death in order to avoid contamination on the basis of anniversary grief reactions.

Data safety and management plan

An independent Data and Safety Monitoring Board (DSMB) will be organized to ensure patient safety throughout the trial as well as its validity and scientific merits. The DSMB will comprise a biostatistician experienced in statistical methods for clinical trials, a nursing researcher experienced in conducting randomized controlled trials, and a physician-scientist experienced in cancer care. The DSMB will monitor and address the following issues: (1) sufficient and appropriate enrollment of subjects, including compliance with the eligibility criteria for each dyad of terminally ill cancer patients and family caregivers, (2) appropriate

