The effectiveness of the intervention will be examined using intention-to-treat analyses with generalized estimating equations (GEE) or hierarchical generalized linear modeling (HGLM). Effectiveness of the intervention will be assessed in terms of (1) facilitating prognostic awareness, EOL care discussions, patient-caregiver agreement on preferences for EOL care, and congruence between patients' preferred and actual EOL care, (2) improving patients' and family caregivers' QOL, anxiety and depressive symptoms before the patient's death, and family caregiver bereavement outcomes, and (3) limiting aggressive healthcare resource utilization at EOL. In the intention-to-treat analyses, all participants will be analyzed in the study group to which they are initially allocated, regardless of whether they complete or withdraw from the study. The GEE/HGLM uses robust standard error estimates to take into account (1) within-subject correlations of the outcome variables during the study period, (2) unequal numbers of assessments among subjects, and (3) potential missing observations. In GEE/HGLM analysis, incompleteness of the outcome variables has only marginal influence on the results of longitudinal data analysis because GEE/HGLM involves fitting a generalized linear model to the marginal distribution of repeated outcomes.¹⁵¹

The congruence between terminally ill cancer patients' preferred and actual EOL care will be determined by comparing the agreement between preferences for EOL care elicited at the last assessment and actual EOL care. Preferences for each EOL care treatment will be dichotomized so that those who are "unsure" whether prefer a specific EOL care treatment will be counted as desiring that treatment because in most instances the clinical default is to provide

treatment unless specifically refused.⁷² In addition to the percentage of overall agreement, kappa coefficients will be computed to correct for the amount of agreement that can be expected by chance alone.¹⁵²

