Subsequently, multivariate logistic regression with the GEE method will be used to examine the impact of the ACP intervention on improving the congruence between patients' preferred and actual EOL care, and on secondary outcomes--increasing prognostic awareness, EOL care discussions, and patient-caregiver agreement on preferences for EOL care, and decreasing aggressive healthcare resource utilization at EOL, with simultaneous adjustment for time-varying and invariant confounding factors. The GEE model will also be used to examine the moderation effects of prognostic awareness, EOL care discussions, and patient-caregiver agreement on preferences for EOL care on the ACP intervention's effectiveness in increasing the congruence between patients' preferred and actual EOL care and in decreasing aggressive healthcare resource utilization at EOL.

Multivariate multiple regression with the GEE/HGLM method will be used to test the effectiveness of the ACP intervention in improving patients' and family caregivers' QOL and psychological well-being (depressive and anxiety symptoms) before the patient's death, and family caregiver bereavement outcomes (including QOL, depressive symptoms, and grief reactions), with simultaneous adjustment for time-varying and invariant confounding factors. The GEE/HGLM model will also be used to examine the moderation effects of prognostic awareness, EOL care discussions, patient-caregiver agreement on preferences for EOL care, aggressive healthcare resource utilization, and the extent of congruence between patients' preferred and actual EOL care on the ACP intervention's effectiveness in improving patients' and caregivers' QOL, anxiety and depressive symptoms before the patient's death and facilitating family caregiver bereavement adjustment.

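### For event-dependent treatments, the congruence score treats 'wanted, not received' the same as 'refused, received', so it can differ between arms when the care received is identical

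*Combined protocol and SAP*

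**What the plan says.** The first primary objective in Specific Aims is to "increase the congruence between terminally ill cancer patients' preferred and actual end-of-life (EOL) care". The Statistical analysis plan determines congruence by "comparing the agreement between preferences for EOL care elicited at the last assessment and actual EOL care". Each preference is dichotomised, and a patient who is unsure "will be counted as desiring that treatment because in most instances the clinical default is to provide" it. The summaries are percent agreement and, as a chance correction, kappa: "In addition to the percentage of overall agreement, kappa coefficients will be computed to correct for the amount of agreement that can be expected by" … For the arm comparison, "multivariate logistic regression with the GEE method will be used to examine the impact of the ACP intervention on improving the congruence", so congruence enters as a binary outcome.

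Three other places bear on the point:

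- Data collection procedures says that after death "a chart review and postmortem interview with patients' caregivers will be performed to confirm the type of medical care received at the EOL". It does not mention recording whether a treatment was indicated or offered.
- Components of the proposed study arms describes a physician feedback form, built from interview responses, that reports "when or if the patient/family caregiver prefers to receive ICU care, CPR, intubation with mechanical ventilation support", among other treatments.
- The Sample size calculation gives low receipt rates for patients with and without a care discussion, for example "mechanical ventilation support (1.6% vs 11.0%; AOR, 0.26; 95% CI, 0.08-0.83), and ICU care (4.1% vs 12.4%; AOR, 0.35; 95% CI, 0.14-0.90").

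The plan has no category for a wanted treatment whose occasion never arose, and it does not report the two directions of disagreement separately.

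**The concern.** Whether a patient receives ICU care, CPR, ventilation or hemodialysis depends on a clinical event as well as on the patient's wish. Someone who says yes to hemodialysis and dies without renal failure has had no wish overridden, yet falls in the same disagreement cell as someone ventilated against a refusal. This applies to definite yes answers and is separate from the coding of unsure, although that coding enlarges the affected group.

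The comparison between arms is what is at stake. The intervention uses a workbook, a video and repeated conversations to help participants judge what intensive treatment can achieve, so it is meant to move preferences. If fewer intervention patients end up saying yes or unsure, their scored congruence rises even if exactly the same care is delivered in both arms. The result could then be read as showing that wishes were better honoured.

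**Working it through.** **Inputs.** Receipt rates *r* come from the Sample size calculation: CPR 0.8% and 6.7%, ventilation 1.6% and 11.0%, ICU care 4.1% and 12.4%. The share scored as wanting a treatment (yes or unsure), *w*, is not in the documents. I assume values from 20% to 50%. I also assume that nobody is treated against a refusal.

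**1. The plan's own figure.** For two proportions with two-sided alpha 0.05 and 80% power, take n = [1.96·√(2p̄(1−p̄)) + 0.8416·√(p₁(1−p₁)+p₂(1−p₂))]²/d², then apply the continuity correction n/4·[1+√(1+4/(nd))]².

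- CPR: 161.6, corrected 194.0
- Ventilation: 103.7, corrected 124.05
- ICU care: 171.3, corrected 194.6

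This matches the stated 124-195 per group up to rounding. The sizing therefore fits the receipt rates. The documents cite an odds ratio of 2.26 for congruence but no baseline congruence rate, so receipt rates are the only anchor available here.

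**2. Agreement for one treatment.** With no unwanted care and r ≤ w, the four cells are:

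- wanted and received: r
- wanted, not received: w − r
- refused, received: 0
- refused, not received: 1 − w

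Agreement = r + (1 − w) = 1 − (w − r).

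| Treatment, r | w = 20% | w = 30% | w = 50% |
|---|---|---|---|
| CPR, 0.8% | 80.8% | 70.8% | 50.8% |
| CPR, 6.7% | 86.7% | 76.7% | 56.7% |
| Ventilation, 11.0% | 91.0% | 81.0% | 61.0% |
| ICU care, 12.4% | 92.4% | 82.4% | 62.4% |

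No patient in any row was treated against a refusal.

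**3. Arm contrast with identical care.** Hold CPR receipt at 6.7% in both arms and let only w differ.

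- w = 50%: 1 − (0.50 − 0.067) = 56.7%
- w = 35%: 1 − (0.35 − 0.067) = 71.7%
- OR = (0.717/0.283)/(0.567/0.433) = 2.534/1.309 = 1.93, with about 87% power at 195 per group

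For ICU care at 12.4% in both arms, the same shift gives 62.4% and 77.4%, OR 2.06.

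**4. Kappa.** Kappa = (po − pe)/(1 − pe), with pe = wr + (1−w)(1−r). In the CPR example:

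- w = 50%: pe = 0.500, kappa = 0.067/0.500 = 0.13
- w = 35%: pe = 0.023 + 0.606 = 0.630, kappa = 0.087/0.370 = 0.24

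Kappa moves with w too, and it does not distinguish the two kinds of disagreement.

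**5. How small it can be.** A shift from 30% to 25% with CPR at 6.7% gives 76.7% and 81.7%, OR 1.36, with 23% power at 195 per group. As w approaches r, the cell w − r goes to zero and the effect with it.

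**6. Perfect honouring.** Suppose need arises in 10%, patients who want hemodialysis get it whenever needed, and patients who refuse never do. Agreement is (1 − w) + 0.10w: 64% at w = 40%, 82% at 20% and 95.5% at 5%. Every wish was honoured in all three cases.

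**The case against.** Several points on the other side stand.

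- **Size.** It rests on w and on need, neither of which the documents give. Setting unwanted care to zero makes the score depend only on w and r. A reader might infer that most scored incongruence is artefact, or that the endpoint mainly tracks how many patients say yes. The documents do not support either: they give no share wanting each treatment and no rate of care against refusal. In the 5% case of step 6 the loss is only 4.5 points.
- **Intended mechanism.** A shift towards preferences that fit the likely care is part of what the intervention aims for. It may be a legitimate benefit, but it differs from care changing to follow a wish.
- **Source of the conditional wording.** It describes the feedback form, not the outcome instrument, whose wording is not in the document. The one sentence on chart review is not a field list either. The scoring problem follows from the agreement definition and needs neither text.
- **CPR as the example.** Treating every wanted-but-not-received case as never called for is least plausible for CPR, since cardiac arrest accompanies every death. Some of these cases are true unmet wishes. The contrast in step 3 still arises with identical receipt, and ICU care shows the same pattern.
- **Scope and kappa.** Goals of care and hospice are less affected. Kappa is a descriptive addition; the planned arm test is the logistic GEE.

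**Conclusion.** The point holds for event-dependent treatments. As defined, congruence cannot separate care given against a refusal from a wanted treatment that was not given, and it cannot separate treatments withheld from those never called for. It can therefore differ between arms through preferences alone. Under the stated assumptions (no unwanted care, CPR receipt 6.7% in both arms, share wanting it 50% against 35%), agreement goes from 56.7% to 71.7%, OR 1.93. If the share wanting a treatment is close to its receipt rate, little remains.

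A reader might go further and conclude that the planned primary analysis should be replaced by one that counts a wanted treatment as unmet only when the chart shows it was needed. The documents do not support that step. Need would be a post-randomisation judgement, and an intervention that changes goals of care may change what is worked up and charted. What is missing is a prespecified breakdown by direction, and it should be added because the first primary objective is interpreted through it.

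**What to change.** Keep the planned agreement analysis. In the Statistical analysis plan, prespecify for ICU care, CPR, ventilation and hemodialysis a by-arm report, among all randomised decedents with a last preference and known care received, of:

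- (a) treatment received although the last preference was refusal;
- (b) treatment wanted or unsure but not received;
- the share refusing.

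State that a claim that ACP led to wishes being honoured must be supported by (a), and not only by a shift in preferences. In the CPR example of step 3, this report would show (a) 0% in both arms, (b) 43.3% and 28.3%, and refusal 50% and 65%, which makes the source of the difference plain.

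Optionally, record at the planned chart review whether each treatment was indicated or offered, by a fixed abstraction rule applied blind to arm. Use it only in a sensitivity analysis of (b).

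The core change uses data already collected and costs a few extra tables. Counts in (a) will be low: (a) cannot exceed total receipt, which for CPR at 195 per group is 195 × 0.067 = 13 patients at the higher rate and 195 × 0.008 = 1.6 at the lower. The optional item adds abstraction work, and indication may be charted differently between arms.

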give terminally ill cancer patients and family caregivers a workbook and a video with educational materials on how to manage common symptoms and a list of available resources, including patient support organizations, as well as support and financial assistance through the hospital's social work department. We hypothesize that using a workbook and a video with content on symptom management alone will not impact the outcomes, but parallelize education received by the control group as much as possible with that of the intervention group. This hypothesis is based on a recent systematic review that found using passive informative material in isolation was an ineffective method for promoting use of ACP.¹¹⁹ The attention-control interventionist will visit and interact with participants in the attention-control group according to the same schedule as for the ACP intervention group to assess their symptom distress and general well-being. Necessary referrals to physicians or social workers will be made for further management.

Randomization

We will enroll and randomly assign eligible dyads of terminally ill cancer patients and their family caregivers into either the ACP intervention or the attention-control group in a 1:1 fashion without stratification. Dyad allocations into the two study arms will be concealed from the personnel responsible for recruiting subjects. A randomization schedule using a computerized random number generator will be prepared in advance by a co-PI ([name]) who will have no contact with any participants throughout the trial and will not be involved in recruiting, enrolling, assigning, assessing, or treating them. The sequence of randomization will be sequentially numbered and sealed in opaque envelopes which will be used later by the PI to allocate participants. The PI will be the only person with access to the allocation schedule during the study and will not be involved in recruiting, enrolling, assessing, or treating participants. The sealed opaque envelopes will not be opened until the PI responsible for assigning participants to the two study arms receives a call from the data collector who has completed the recruitment and initial assessment of a patient-caregiver dyad. The PI will then

open the sealed envelope, assign this dyad to the proper study arm, and forward their information from the envelope to the ACP or attention-control interventionist, accordingly.

Blinding

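### Both effectiveness clauses adjust the arm effect for unnamed time-varying factors without excluding variables that ACP is meant to change, so the coefficient need not be the total effect of allocation

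*Combined protocol and SAP*

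**What the plan says.** The Statistical analysis plan has two effectiveness clauses. The first uses logistic GEE for congruence and the secondary outcomes. The second uses GEE/HGLM regression for QOL and mood before death and for caregiver bereavement outcomes. Both models are fitted "with simultaneous adjustment for time-varying and invariant confounding factors". No section lists these factors or restricts them to baseline values. Intention-to-treat is defined only as analysing participants in the group to which they were allocated.

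Under Randomization, the envelope stays sealed until the PI "receives a call from the data collector who has completed the recruitment and initial assessment of a patient-caregiver dyad". Allocation therefore follows the first assessment.

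Specific Aims states what ACP should change. It should "facilitate terminally ill cancer patients' prognostic awareness; EOL care discussions among patients, family caregivers, and physicians", and it should "improve QOL, depressive and anxiety symptoms of patients and family caregivers during the patient's dying process".

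The plan then adds moderation models. For QOL, anxiety and depression before death and for bereavement adjustment, the listed moderators include aggressive healthcare resource utilisation and the extent of congruence. Congruence is obtained by "comparing the agreement between preferences for EOL care elicited at the last assessment and actual EOL care". Data collection procedures adds that after death "a chart review and postmortem interview with patients' caregivers will be performed to confirm the type of medical care received at the EOL".

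**The concern.** In a randomised comparison, variables fixed before allocation can be adjusted for safely. A variable measured afterwards may be a consequence of arm. If it is, entering it in the model removes or distorts the part of the effect that runs through it. The coefficient then no longer answers the question the trial was randomised to answer.

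The trial assesses participants every 3 weeks and intends ACP to shift several of the variables collected, so candidate covariates of this kind will be in the dataset. The two clauses cover all the primary objectives. Because the list is open, the choice could also be made after the data are seen.

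The moderation models do not alter the main estimate. They do raise a narrower question of time order: a moderator must have a value when the outcome it is said to modify is measured.

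**Working it through.** No figure stated in the plan is challenged, so there is none to reproduce. The check is one of reading and timing, followed by one illustration.

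**1. What the clause allows.** It names time-varying factors as well as invariant ones. Values that change over follow-up are, apart from their first measurement, post-allocation values. Nothing limits them to factors that arm cannot affect.

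**2. Timing.** The order is initial assessment, then allocation, then follow-up. A later value affected by arm lies downstream of allocation and is not a confounder of it.

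**3. Does analysis by allocated group help?** No. It fixes which group a dyad is counted in. It does not govern which covariates sit beside the arm term.

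**4. Illustration (congruence).** Inputs:
- direct arm odds ratio 1.5 (assumed);
- ACP-to-covariate odds ratio 2 (assumed);
- covariate-to-congruence odds ratio 2.26. The size is borrowed from the association between EOL care discussions and congruence cited under Sample size calculation; its use here is an assumption;
- control covariate rate 40% and control congruence 50% (assumed);
- no unmeasured common cause of covariate and congruence (assumed).

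Write expit(x) = 1/(1+e^(−x)).

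- Covariate rate under ACP: odds 2 × 0.40/0.60 = 1.333, so the rate is 1.333/2.333 = 0.571.
- Intercept c solves 0.60·expit(c) + 0.40·expit(c + ln 2.26) = 0.50, giving c = −0.324. Control congruence is 0.420 without the covariate and 0.620 with it (0.60 × 0.420 + 0.40 × 0.620 = 0.500).
- Multiplying those odds by 1.5 gives 0.5204 and 0.7103 under ACP.
- Overall ACP congruence: 0.4286 × 0.5204 + 0.5714 × 0.7103 = 0.6289.
- Unadjusted arm odds ratio: (0.6289/0.3711) ÷ (0.50/0.50) = 1.695.
- Adjusted arm odds ratio: 1.500 by construction. On the log scale, 0.405/0.528 = 0.77, so adjustment removes about 23%.

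Two checks:
- *Non-collapsibility.* With an ACP-to-covariate odds ratio of 1, ACP congruence is 0.60 × 0.5204 + 0.40 × 0.7103 = 0.5963. The unadjusted odds ratio is 0.5963/0.4037 = 1.477, against 1.500 adjusted. That shift is small and in the other direction, so it does not explain the drop from 1.695.
- *Direction.* With a covariate-to-congruence odds ratio of 0.5 and the other inputs unchanged, the pair is 1.318 unadjusted and 1.500 adjusted. Adjustment can therefore move the estimate either way.

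**5. Moderators and time order.**

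| Listed moderator | When its value exists | Outcomes before death |
|---|---|---|
| Congruence | Once actual EOL care has been received; confirmed after death | Its value does not yet exist |
| Aggressive utilisation | Can occur during follow-up: the ACP Intervention section lists ICU admission and mechanical ventilation as events that trigger a further intervention course | Can precede a later assessment |

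The time-order objection is decisive for congruence. For utilisation it depends on how the variable is defined.

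**The case against.** The strongest reply is that this is an ambiguity and not a demonstrated error. A reader might infer that the plan will adjust for prognostic awareness, EOL care discussions or mood, and so will bias the arm effect. The documents do not support that. Awareness, discussions and patient-caregiver agreement have their own moderation models, which suggests they lie outside the set of confounders. The 3-week schedule was chosen "to cover the most rapid change of patient physical conditions and demanding period of caregiving until the death of the patient", so physical condition, caregiving demand or simply time may be what is meant. The first clause also joins congruence, which is determined once, with repeatedly assessed outcomes, and the time-varying part may be intended only for the latter. All of this stands as a limit on what can be claimed about consequences. It does not close the gap: none of these readings is written as a restriction, and the moderation models leave QOL and mood free to enter as covariates.

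A second reply is that assessments "continue until patient death, loss to follow-up, study withdrawal, or when the patient can no longer be interviewed", so those still assessed may no longer be comparable between arms, and later variables could help there. That is a separate missing-data question. It does not justify placing variables affected by arm in the main effect model, and resolving the present point does not require a new missing-data analysis.

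A reader might also infer that aggressive utilisation, like congruence, cannot moderate outcomes before death. The moderation sentence does not confine utilisation to the end of life, and such care can occur earlier, so that inference fails.

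**Conclusion.** The point holds as a gap in specification that should be fixed. It is certain that the wording permits adjustment for post-allocation variables affected by arm, and that no baseline-only or unadjusted main model is named. Whether such a variable will be entered is unknown. So are the direction and size of any departure from the total effect, which could be negligible. The change from 1.695 to 1.500 shows only the mechanism. It rests entirely on the assumed inputs and does not estimate what this trial would see.

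The moderation point is separate and lesser. As written, using congruence to moderate QOL, anxiety and depression before death is wrong in time order. For every moderator measured after allocation, arm contrasts within its levels are not randomised comparisons.

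**What to change.** In both effectiveness clauses, limit the main arm-effect models to:
- arm;
- a pre-specified, named list of covariates measured before allocation, including the baseline value of the outcome where one exists;
- assessment time, or other terms that arm cannot affect.

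Label any model with other post-allocation covariates secondary or exploratory.

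Separately, remove congruence as a moderator of QOL, anxiety and depression before death. If aggressive utilisation is kept for those outcomes, use only utilisation that occurred before each assessment. Label all moderation analyses by post-allocation variables exploratory.

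The cost is a change of wording. The initial assessment already precedes allocation, and the plan already compares baseline characteristics and outcomes, so the main models need no new data and the target of 231 dyads per group is unaffected. The downsides are fewer confirmatory moderation claims, and some lost precision if a strong later prognostic factor that arm does not affect is left out.
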